9.6 Data Analysis

9.6.1 Planned Analyses

9.6.1.1 Primary Analysis

Incidence of hypocalcemia will be examined during the first 12 months following cinacalcet initiation overall and according to disease severity as defined by three hypocalcemia thresholds: < mild ($\geq 8.0 - < 8.4$ mg/dL), moderate ($\geq 7.5 - < 8.0$ mg/dL), and severe (< 7.5 mg/dL).

After identifying patients who develop hypocalcemia, sub-analyses of hypocalcemia patients will be carried out to describe cinacalcet prescribing practices (i.e. reduced dose or discontinuation) and treatment patterns of other conventional therapies for SHPT during the 12 months following hypocalcemia event.

Among patients who discontinued cinacalcet, another sub-analysis will be carried out to determine rate of cinacalcet re-initiation and to identify factors associated with re-initiation as well as describe treatment patterns prior to re-initiation during the 12 months following cinacalcet discontinuation.

9.6.2 Planned Method of Analysis

9.6.2.1 Descriptive Analysis

Baseline characteristics of patients who do vs. do not develop hypocalcemia until end of follow-up of 12 months will be summarized for patients who initiate cinacalcet using descriptive statistics. Summary statistics will be presented for the time-varying covariates of Table 2 for the 90 days prior to initiation, discontinuation and re-initiation for cinacalcet. Continuous variables will be described using the mean and standard deviation, median, 25th and 75th percentiles and minimum and maximum values. Ordinal or skewed variables will be described using a median and range or categorized into meaningful categories at which point categorical data analysis will be applied. Categorical data will be reported as counts and frequencies.

Summary statistics will also be presented for time to first hypocalcemia event, time to any treatment intervention following hypocalcemia event, and time to cinacalcet re-initiation. In addition, cinacalcet prescribing patterns at initiation, at time of hypocalcemia event and after hypocalcemia event and treatment patterns (e.g. vitamin D, phosphate binders and CVD medications) 90 days prior to cinacalcet initiation, at time of cinacalcet initiation, at time of hypocalcemia event, and time of cinacalcet re-initiation will be described. Number of HD patients who initiate cinacalcet with hypocalcemia (<8.4 ng/mL) amongst all cinacalcet users will also be counted.

Plot median and IQR of PTH, calcium and phosphate values every month or quarter during the 12 months following cinacalcet initiation, following hypocalcemia event and following cinacalcet re-initiation. The resulting data will be arranged graphically, stratified by levels of control (Table 3) during the baseline period, to depict the longitudinal pattern of laboratory values following initiation, discontinuation and re-initiation of treatment.

Smoothing techniques may need to be employed to fit the patterns of the laboratory data trajectory.

Table 3. Levels of control

	Serum PTH (pg/mL)	Serum Calcium (mmol/L)	Serum Phosphate (mmol/L)
Low	<150	<2.10	<1.13
Medium	Medium low 150<300	2.10-<2.37	1.13-<1.78
	Medium high 300-<600		
High	≥600	≥2.37	≥1.78

9.6.2.2 Analysis of the Primary, Secondary and Exploratory Endpoint(s)

9.6.2.3 Primary and secondary objective endpoints

Point estimates and 95% confidence intervals will be derived to determine the rate of hypocalcemia following cinacalcet initiation, rate of cinacalcet discontinuation following hypocalcemia event and rate of cinacalcet re-initiation following discontinuation due to hypocalcemia.

Time to first hypocalcemia event, time to any treatment intervention following hypocalcemia event, and time to cinacalcet re-initiation will be estimated using Kaplan-Meier methods according to baseline calcium levels (i.e. mild, moderate or severe) at baseline.

Cox regression models will be used to identify baseline covariates (Table 2) associated with time to first occurrence of hypocalcemia during the first 12 months of the study, time to any treatment intervention during the 12 months following hypocalcemia event and time to cinacalcet re-initiation during the 12 months following cinacalcet discontinuation. Subjects who do not experience hypocalcemia will be censored (according to 9.2.4.1 criteria). Univariate analysis will be performed. Variables significant at the 0.25 level in univariate analysis will be entered into a multivariate analysis using a stepwise regression technique (significance levels of 0.10 for inclusion/exclusion). Hazard ratios and 95% confidence intervals will be presented.

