7.1 Diseases and Therapeutic Area

Secondary hyperparathyroidism (SHPT) is a common complication of chronic kidney disease (CKD) (Goodman, 2004). As kidney function declines this causes disturbances

in the balance of calcium, phosphorous and vitamin D and consequently cause CKD-related mineral and bone disorders (CKD-MBD). These biochemical imbalances of increased calcium, phosphate lead to an overproduction of parathyroid hormone (PTH) and parathyroid gland hyperplasia which characterizes SHPT. Elevated levels of PTH can develop at early stages of CKD even when calcium and phosphorous are within normal range limits (Martinez *et al*, 1997). The impact of SHPT on progressive CKD results in bone mass reduction and an impaired rate of bone remodeling. This inadequate control of SHPT can consequently lead to increased risks of vascular calcification, fractures and cardiovascular morbidity and mortality (Horl, 2004). Approximately 30-47% of severe CKD patients on dialysis in Europe are affected with SHPT (PTH>300 pg/mL) (Hedgeman *et al*, 2015).

Prevention and treatment of SHPT remains a challenge although successful management can be partially achieved with standard treatment with dietary phosphate restriction, phosphate binders, vitamin D and parathyroidectomy. However, the introduction of calcimimetic agents has provided an alternative therapeutic option to manage SHPT. Calcimimetics acts as an allosteric activator by selectively binding to calcium-sensing receptors (CaSR) in the parathyroid gland which lowers the CaSR action of extracellular calcium ions on PTH secretion; and thereby reducing PTH levels and accompanying serum calcium levels (Rodriguez *et al*, 2015).

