8.2 Secondary objectives

HD patients with cinacalcet prescription and serum calcium >8.4 mg/dL at baseline

(Cohort B)

- 8.2.1 To determine the incidence of hypocalcemia in SHPT patients with CKD on HD following cinacalcet initiation
- 8.2.2 To determine the frequency of hypocalcemia events in cinacalcet patients
- 8.2.3 To determine time to first hypocalcemia event
- 8.2.4 To describe characteristics of cinacalcet patients who develop and who do not develop hypocalcemia
- 8.2.5 To identify factors associated with time to hypocalcemia event in cinacalcet patients

Hypocalcemia HD patients who discontinued cinacalcet prescription (Cohort C)

- 8.2.6 To determine time to cinacalcet re-initiation
- 8.2.7 To determine the rate of cinacalcet re-initiation among patients who discontinued cinacalcet following hypocalcemia event
- 8.2.8 To describe factors associated with time to cinacalcet re-initiation event in patients who discontinued cinacalcet following hypocalcemia event
- 8.2.9 To describe treatment patterns (e.g. vitamin D, phosphate binders and CVD medications) at time of hypocalcemia event, at time of discontinuation, and at time of cinacalcet re-initiation
- 8.2.10 To describe the trajectory of PTH, calcium and phosphate values following cinacalcet initiation, following hypocalcemia event, and following cinacalcet re-initiation

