9.2.2 Subject/Patient/Healthcare Professional Eligibility

9.2.2.1 Inclusion/Exclusion Criteria

Inclusion criteria

HD patients in AROii cohort i) aged ≥ 18 , ii) filled a cinacalcet prescription after 01 January 2007, iii) enrolled in AROii for at least 90 days prior to cinacalcet initiation and have at least 90 days follow-up following cinacalcet initiation (*Cohort A*). HD patients who have serum Ca ≥ 8.4 mg/dL at time of cinacalcet initiation will be included in subsequent analyses (*Cohort B*). A sub-set of HD patients who develop hypocalcemia (serum Ca < 8.4 mg/dL) will define *Cohort 1* which will be used to evaluate the primary objectives. HD patients with hypocalcemia who discontinued cinacalcet will be included in further sub-analyses (*Cohort C*).

Exclusion criteria

Patients with i) parathyroidectomy up to and including the first 90 days of follow-up, ii) a prescription for cinacalcet is less than 15 days (2 weeks) with no further prescriptions

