9.3.1.2 Development of hypocalcemia

Patients who developed hypocalcemia as defined by serum calcium <8.4 mg/dL.

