9.3.2 Outcome Assessment

Table 1 summarizes the outcomes to be assessed according to each objective.

Table 1. Outcomes for analysis

Objective	Definition
PRIMARY OBJECTIVES	
Hypocalcemia HD patients with cinacalcet prescription	
- Rate of cinacalcet discontinuation	- Number of patients who discontinue cinacalcet. Discontinuation is defined as the time point beyond which there were ≥ 90 consecutive prescription-free days.
-Cinacalcet prescribing pattern	- No change, dose reduced (relative to dose prior to hypocalcemia), discontinued, Dose increased (relative to dose prior to hypocalcemia)
- Prescribing pattern for any treatment and each of the following drugs: paricalcitol, older AVD, phosphate binder, dialysate calcium and CVD medications	- No change, dose reduced (relative to dose prior to hypocalcemia), discontinued, Dose increased (relative to dose prior to hypocalcemia)
SECONDARY OBJECTIVES	
HD patients with cinacalcet prescription	
- Incidence of hypocalcemia	- First occurrence of a serum calcium (< 8.4 vs. ≥ 8.4 mg/dL) - First occurrence of serum calcium defined by severity: mild (serum calcium ≥ 8.0 - < 8.4 mg/dL), moderate (serum calcium ≥ 7.5 - < 8.0 mg/dL), severe (serum calcium < 7.5 mg/dL)
Hypocalcemia HD patients who discontinued cinacalcet prescription	
- Rate of cinacalcet re-initiation	- Number of patients who re-initiate cinacalcet prescription following discontinuation (yes/no)
- Prescribing pattern for each of the following drugs: cinacalcet, paricalcitol, older AVD, phosphate binder, dialysate calcium and CVD medications	- No change, dose reduced (relative to dose prior to hypocalcemia), discontinued, Dose increased (relative to dose prior to hypocalcemia)
EXPLORATORY OBJECTIVES	
- Incidence of hypocalcemia by PTH	- No. of patients with hypocalcemia according to PTH levels: low (< 10 ng/L or pg/mL), normal (10-65 ng/L or pg/mL) or high (> 65 ng/mL or pg/mL)
- Kinetics of hypocalcemia	- Progressors (subsequent events were more severe than initial events), remitters (subsequent events were less severe than initial events), fluctuators (events ranged in severity with no trend in one direction)
- Changes in calcium level	- Changes in mean or median calcium levels following changes in treatment treatment
- Cardiovascular event	- Any coronary artery event (CVE), cerebrovascular event (CVE), peripheral arterial event (PAE), congestive heart failure event (CHFE), or sudden cardiac event (SCE)

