Laboratory parameters	Hemoglobin [g/dL]	<10, 10-<12, ≥12	baseline
	Ferritin [µg/L]	<500, ≥500	baseline
	CRP [mg/L] *	Quartiles	baseline
	Serum albumin [g/L] *	Quartiles	time-varying
	Creatinine [µmol/L] *	Quartiles	baseline
	Total calcium [mmol/L]	<2.10, 2.10-2.37, >2.37	time-varying
	Phosphate [mmol/L]	<1.13, 1.13-1.78, >1.78	time-varying
	Alkaline phosphatase	<44 IU/mL, 44-147 IU/mL (normal), >147	time-varying

	PTH [pg/mL]	<150, 150-<300, 300-<600, ≥600	time-varying
Medication use	Cinacalcet use [§]	Yes/No	time-varying
	Paricalcitol use [§]	Yes/No	time-varying
	Older AVD use [§]	None; Alfacalcidol; Calcitriol; both	time-varying
	Phosphate binder use [§]	None, Only calcium-based, Only non calcium-based, Any	time-varying
	Cardiovascular medication [§]	Yes/No	time-varying

01 August 2009. If the baseline period or the interval corresponding to the time-varying analysis includes the publication of the KDIGO guidelines, then the value of the value of exposure period pre-KDIGO covariate will be set to Yes; [§] relevant ATC codes in Appendix B; ^{} The quartiles' cut-offs for these variables will be derived at baseline.

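### The Kaplan-Meier strata for time to first hypocalcemia cannot contain any Cohort B patient, and the Table 1 PTH bands hardly divide the population

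*Protocol*

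**What the plan says.** Calcium strata:

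- Section 9.6.2.3 covers three Kaplan-Meier endpoints in one sentence: time to first hypocalcemia, time to any treatment intervention, and time to cinacalcet re-initiation. All are to be estimated "according to baseline calcium levels (i.e. mild, moderate or severe) at baseline".
- Table 1 and sections 9.3.2.1, 9.6.1.1 and 9.6.2.6 define mild as 8.0 to below 8.4 mg/dL, moderate as 7.5 to below 8.0, and severe as below 7.5.
- Time to first hypocalcemia is objective 8.2.3, in Cohort B. Section 9.2.2.1 requires calcium of at least 8.4 "mg/dL at time of cinacalcet initiation will be included in subsequent analyses". Section 8.2 describes the same cohort as "HD patients with cinacalcet prescription and serum calcium >8.4 mg/dL at baseline".
- The event itself (9.3.1.2) is: "Patients who developed hypocalcemia as defined by serum calcium <8.4 mg/dL".

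PTH strata:

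- Table 1, for incidence by PTH, uses low below 10, "normal (10-65 ng/L or pg/mL) or high" above 65. The unit in the top band is ng/mL or pg/mL.
- Tables 2 and 3 use below 150, 150 to below 300, 300 to below 600, and 600 or more pg/mL.
- Section 7.1 reports the share of European dialysis patients who "are affected with SHPT (PTH>300 pg/mL" and cites a guideline target range of 150 to 300 pg/mL.

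**The concern.** The severity words describe a hypocalcemia value. In 9.6.2.3 they are applied to baseline calcium in a cohort selected for not having hypocalcemia. Whoever programs the curve must then choose other strata with the retrospective data already in hand.

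One easy repair would do harm. Grouping Cohort B by the severity of the event that later occurs is grouping by the outcome: patients without an event have no group, and every patient in a group has the event, so each event-free curve must fall to zero.

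For PTH, objectives 8.3.2 and 8.3.3 exist only to compare hypocalcemia across PTH levels. The Table 1 cut-points put a patient who is inside the cited guideline target in the same top band as one at 600 pg/mL or more, so the comparison has almost nobody on its other side.

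**Working it through.** The plan gives no figure for stratum sizes, so there is none to reproduce on this point. Its study-size figures do reproduce: 1245 × 0.47 = 585, stated as about 600, and 1.96 × √(0.25/600) = 0.040. Neither depends on the strata.

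**Calcium, Cohort B.** Overlap of each stratum with the entry range of 8.4 mg/dL and above:

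- mild, 8.0 to <8.4: none
- moderate, 7.5 to <8.0: none
- severe, <7.5: none

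The result is the same with the entry limit written as ≥8.4 (9.2.2.1) or >8.4 (8.2, 9.2.4). Section 9.3.3 takes the baseline value as the last one in the baseline period, and 8.2 states the calcium limit at baseline. I therefore treat the value that admits a patient and the value that stratifies as the same.

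**Bands that Cohort B can fill.** With 1 mmol/L = 4.008 mg/dL (assumed; the protocol gives no factor):

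- 2.10 × 4.008 = 8.42 mg/dL
- 2.37 × 4.008 = 9.50 mg/dL
- 8.4 / 4.008 = 2.096 mmol/L

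The Table 3 medium and high bands are both available to Cohort B. The low band overlaps the entry range only from 8.40 to 8.42 mg/dL, so it is nearly but not strictly empty: a patient at exactly 8.4 mg/dL (admitted under ≥8.4) falls in it.

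**Calcium, Cohort 1.** Baseline runs from initiation to development of hypocalcemia (9.2.3). The text does not say whether the index value closes that period.

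- If it does, every baseline value is below 8.4 mg/dL, that is below 2.096 mmol/L. The severity strata then work, but every patient sits in the lowest of the Table 2 bands ("<2.10, 2.10-2.37, >2.37") at baseline.
- If it does not, the last value must be at least 8.4 mg/dL, or it would itself have been the first event. The two upper Table 2 bands then work, but the severity strata are empty.

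On either reading, the Table 2 bands at baseline do not carry event severity into the Cox model.

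**Calcium, Cohort C.** Baseline ends at discontinuation, when calcium may have recovered. Such a patient has no place in a mild, moderate or severe grouping of the baseline value.

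**PTH.** No criterion in 9.2.2.1 limits PTH, and the protocol gives no PTH distribution. Assume PTH is log-normal with median m and log-SD s. Then P(PTH ≤ 65) = Φ((ln 65 − ln m)/s). Counts are out of 1245, all patients prescribed cinacalcet (9.5); Cohort B is smaller.

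| m (pg/mL) | s | P(≤65) | patients of 1245 |
|---|---|---|---|
| 300 | 0.5 | 0.0011 | 1.4 |
| 300 | 0.8 | 0.0280 | 34.8 |
| 300 | 1.0 | 0.0631 | 78.5 |
| 500 | 0.5 | 0.0000 | 0.0 |
| 500 | 0.8 | 0.0054 | 6.7 |
| 500 | 1.0 | 0.0207 | 25.7 |
| 700 | 0.5 | 0.0000 | 0.0 |
| 700 | 0.8 | 0.0015 | 1.8 |
| 700 | 1.0 | 0.0087 | 10.9 |

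The top band holds between 1 − 0.0631 = 93.7% and almost 100%. In the least favourable row (300, 1.0), P(<10) = 0.000335, or 0.4 patients, so the low band is expected to hold fewer than one.

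**Units.** ng/L and pg/mL are the same. ng/mL is a thousand times larger, so 65 ng/mL is 65,000 pg/mL.

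**The case against.** The best defence is that little is lost. Objective 8.2.3 asks only for time to first hypocalcemia and names no strata; an unstratified curve answers it, and the abstract says only baseline calcium levels. The Cohort B Cox model already contrasts two calcium bands that its patients can fill and carries the 150/300/600 PTH bands. Section 9.6.2.6 reports all primary and secondary analyses by severity. All of this stands, and it limits the point to one stratified secondary curve and two exploratory objectives. It does not make the strata in 9.6.2.3 usable.

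A reader might infer three stronger things that the protocol does not support:

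- That the PTH bands are empty by construction. PTH is not an eligibility criterion, and the 300 pg/mL figure is attached to a cited prevalence in the background, not to a study definition.
- That the study would report nothing on calcium, severity or PTH. The analyses just listed contradict this.
- That all of Cohort 1 falls in one Table 2 calcium band. This holds only if the index value counts as the baseline value, which the text leaves open; total calcium is also time-varying in Table 2.

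**Conclusion.** The calcium contradiction is certain from the text: zero Cohort B patients can enter any of the three strata named for time to first hypocalcemia. It rests on no distributional assumption, only on the entry limit applying to the baseline value, as 8.2 says.

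The PTH point is a poor choice of cut-points, inconsistent with the protocol's own Tables 2 and 3, plus a unit error. That the split is nearly uninformative rests on the assumed log-normal shape, with median 300 to 700 pg/mL and log-SD 0.5 to 1.0.

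For Cohorts 1 and C the severity strata can be filled once they are tied to the index event, which 9.6.2.3 does not do. The point should be fixed before analysis. It does not threaten the primary discontinuation rate, and the study tests no formal hypothesis.

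**What to change.** 1. In 9.6.2.3, stratify the Cohort B curve by two bands: 8.4 mg/dL to <2.37 mmol/L, and ≥2.37 mmol/L. Set the lower edge at 8.4 mg/dL rather than 2.10 mmol/L, so that a patient at exactly 8.4 is not dropped, and use one form of the entry limit (≥8.4 or >8.4) throughout.
2. State that the Cohort 1 and Cohort C curves are stratified by severity of the index hypocalcemia value, consistent with 9.6.2.6.
3. Keep the Table 2 calcium bands, and add index-event severity (mild, moderate, severe) as a separate fixed covariate in the Cohort 1 and C Cox models. Replacing the Table 2 bands with the severity bands would leave patients whose calcium has recovered without a category.
4. In Table 1, use the Table 3 PTH bands (<150, 150 to <300, 300 to <600, ≥600 pg/mL) in one unit, and apply them to 8.3.2 and 8.3.3.

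The cost is a few lines of text using cut-points already in the protocol. The three-level severity covariate adds two parameters per model. This matters most in Cohort C, which may be small: if the roughly 17% discontinuation from the US study in 7.2 applied, 0.17 × 600 = 102 patients.

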9.2 Setting and Study Population

The source population for this study is the AROii cohort, which comprises of adult subjects presenting at one of 304 participating facilities in 14 European countries (*Czech Republic, France, Hungary, Ireland, Italy, Poland, Portugal, Romania, Russia, Serbia, Slovak Republic, Slovenia, Spain, and United Kingdom*) and Turkey enrolled between 01 January 2007 and 31 December 2009. Out of 10,600 patients enrolled, 1876 patients were still on follow-up by the end of 2014.

AROii, a closed-cohort by design, comprises of chronic (ten or more contiguous dialysis sessions) incident (<183 days since commencing renal replacement therapy (RRT)) haemodialysis patients with no history of renal transplantation or peritoneal dialysis. Data are captured electronically via the FMC European Clinical Database (EuCliD) and supplied on a quarterly basis. By Q4 2014, the AROii study population had accrued over 33,000 person-years of follow-up.

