9.5 Study Size

Since this is a study with descriptive objectives, sample size calculations are based on the level of precision (i.e. half width) of the 95% confidence interval (CI) around the point estimate of the proportion discontinuing cinacalcet (p) following development of hypocalcemia. Based on previous analysis by de Francisco et al (de Francisco *et al*, 2016), approximately 1245 HD patients in AROii were prescribed cinacalcet. Based on observational data (Brunelli *et al*, 2015), approximately 47% of patients on cinacalcet are expected to develop hypocalcaemia, so *Cohort 1* is expected to contain approximately 600 patients. The maximum half width of the 95% confidence interval for a proportion based on 600 patients is 0.040.

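### Choosing Cox predictors from all of Table 2 by a 0.25 screen and 0.10 stepwise selection leaves the presented 95% confidence intervals without 95% coverage

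*Protocol*

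**What the plan says.** Section 9.6.2.3 of the Protocol fixes the procedure. "Cox regression models will be used to identify baseline covariates (Table 2) associated with time to first occurrence of hypocalcemia"; the same models are then applied to time to any treatment intervention after hypocalcemia and to time to cinacalcet re-initiation. Each covariate is examined singly. "Variables significant at the 0.25 level in univariate analysis will be entered into a multivariate analysis", built by a "stepwise regression technique (significance levels of 0.10 for inclusion/exclusion". The output is stated plainly: "Hazard ratios and 95% confidence intervals will be presented".

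These models serve primary objective 8.1.4 and secondary objectives 8.2.5 and 8.2.8. Section 7.3 rules out formal hypothesis tests but names hazard ratios and 95% confidence intervals as the inference for the predictor analyses. Section 9.5 sizes only the proportion discontinuing cinacalcet. It gives no event count for any Cox model and no size for Cohort C. Neither section 9.6.2.3 nor the limitations in section 9.8 mentions a core model, shrinkage, resampling, a limit on parameters per event, or caution about intervals after selection.

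**The concern.** An ordinary 95% interval from a Cox model assumes that the model was chosen without looking at the outcome. Here the outcome chooses the model twice, first at 0.25 and then at 0.10. A covariate with no effect reaches the final table only if its estimate happened to lie far from a hazard ratio of 1, so its interval excludes 1 far more often than 5% of the time. A real but modest effect is kept mainly in samples that overstate it, which biases the hazard ratio upward when events are few.

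The three predictor objectives rest on these models. The models would report associated factors almost regardless of whether any exist, in a study that section 7.2 links to treatment guidance on managing hypocalcemia. Section 9.6.2.6 also asks for all primary and secondary analyses by three severity strata, which leaves fewer events for each model.

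**Working it through.** **Inputs**
- Screen 0.25, stepwise 0.10 in and out, 95% intervals: section 9.6.2.3.
- Candidates: Table 2, section 9.3.3. Country has 15 levels, because section 9.2 lists 14 countries "and Turkey enrolled between 01 January 2007 and 31 December 2009".
- Section 9.5: "approximately 1245 HD patients in AROii were prescribed cinacalcet"; "approximately 47% of patients on cinacalcet are expected to develop hypocalcaemia"; Cohort 1 about 600.
- Discontinuation after hypocalcemia about 17% (US observational data, section 7.2). A figure of 22% (US, section 7.1) combines discontinuation with dose reduction.
- Assumption, not in the Protocol: 30 to 70% of Cohort C re-initiate.

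**1. The plan's own figure.** Maximum half width = 1.96 × √(0.25/600) = 0.040, as stated. With 0.47 × 1245 = 585 patients it is 0.0405. The figure is right but says nothing about the Cox models.

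**2. Candidate parameters.** Categories minus one, summed over Table 2 and omitting the blank follow-up row: demographics 19 (country alone 14), clinical 10, aetiology 6, medical events 4, dialysis 10, laboratory 21, medication 9. The total is 79 from 32 covariates, or 78 from 31 if cinacalcet use is dropped as constant.

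**3. Selection by chance alone.** With no true effects and independent covariates, 32 × 0.25 = 8 are expected to pass the screen. The chance that at least one falls below 0.10 is 1 − 0.90^32 = 96.6%.

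**4. Events available.**
- Cohort B: about 585 hypocalcemia events, and 585/79 = 7.4 per parameter.
- Cohort C: 585 to 600 × 17% = 99 to 102 patients. With 22% it is 129 to 132.
- Re-initiation events: from 99 × 0.30 = 30 to 132 × 0.70 = 92, or 30/79 = 0.4 to 92/79 = 1.2 per parameter.

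**5. Simulation of the rule, no true effects.** 78 parameters with Table 2's structure, independent covariates and equal-sized categories; likelihood-ratio screen at 0.25, stepwise at 0.10, Wald 95% intervals from the final model.

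| Patients/events | Runs | Noise covariates kept | Runs keeping any | Coverage of 95% CIs |
|---|---|---|---|---|
| Cohort C, 100/30 | 400 | 4.0 | 97.5% | 60.8% |
| Cohort C, 115/58 | 400 | 3.6 | 97.0% | 59.9% |
| Cohort C, 130/90 | 400 | 3.7 | 97.3% | 61.7% |
| Cohort B, 1245/585 | 60 | 2.8 | 95.0% | 66.5% |

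A separate simulation at about Cohort 1's size (585 patients, 274 events, 60 runs) had 37% of intervals excluding 1, which is 63% coverage.

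**6. Three true binary effects.**
- Cohort C (115/58, true HR 1.5): overall coverage 64%. Selected true factors had coverage 82% and mean log HR 0.788 against 0.405, that is e^0.788 = 2.2 against 1.5. They were selected 508 times out of 400 × 3 = 1200, or 42%.
- Cohort B (1245/585, true HR 1.2): overall coverage 75%. Selected true factors had coverage 98% and mean log HR 0.232 against 0.182, that is 1.26 against 1.20. On average 2.5 noise covariates came with them.

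**7. Models without selection.** Coverage in Cohort C was 95.5% (3 parameters, 30 events), 95.0% (5 and 58) and 93.9% (9 and 90), with mean log HR about 0.43 against 0.405. The full 78-parameter model gave 94.1% in Cohort B. In Cohort C (115/58) it failed: coverage 44.7%, median log HR 2.3 against 0.405.

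**The case against.** The study is descriptive and tests no hypothesis, and its discontinuation proportions, Kaplan-Meier estimates and prescribing patterns do not depend on these models. That is true and limits the reach of the point. It does not rescue the intervals, because section 7.3 makes them the inference for the predictor analyses.

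The low null coverage is partly mechanical. A one-parameter noise covariate kept because p < 0.10 has p < 0.05 about half the time (0.05/0.10), whatever the sample size. This stands: the number of candidates governs how many noise factors appear, not how badly each interval covers. But the selected intervals are the ones the multivariate model presents, so their coverage is what the reader needs.

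A global null is also unlikely. Section 7.1 cites low baseline calcium as predictive of discontinuation. For that reason step 6 adds true effects; overall coverage still reached only 64% and 75%.

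Three stronger readings are tempting and not supported:
- A reader might infer that interval coverage collapses specifically in Cohort C. Under the null it is 60 to 62% there and 67% in Cohort B. What sets Cohort C apart is scarce events and inflated hazard ratios.
- A reader might infer that every interval is too narrow. In Cohort B, selected true factors kept their coverage.
- A reader might infer that parameters certainly outnumber events in Cohort C. That fails if more than 78/129 = 60% or 78/99 = 79% re-initiate, and the Protocol gives no rate.

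Finally, a statistical analysis plan could add reporting cautions, and univariate results may be shown too. The selection rule and the intervals are nevertheless fixed in the Protocol, so this is not a matter merely left open.

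**Conclusion.** The rule as written is unsound for all three predictor objectives. It will almost always yield at least one factor, and under no true effects the intervals labelled 95% cover at about 60 to 67%. For objective 8.2.5 (Cohort B) the main harm is spurious factors beside real ones. For objective 8.2.8 (Cohort C) real effects are also overstated, by roughly 2.2 against 1.5 in the scenario examined.

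The conclusion about coverage rests on simulations with independent covariates and equal-sized categories, and the Cohort B runs were few. Cohort C's size is inferred from US figures. About 100 is better supported than 129, since the 22% includes dose reduction. The 1245 is taken before the eligibility and baseline-calcium criteria of section 9.2.2.1, so the cohort may be smaller still; a different discontinuation rate in this population could move it either way. The event range of 30 to 92 depends on the assumed 30 to 70% re-initiation.

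**What to change.** Remove the 0.25 screen and the 0.10 stepwise rule from section 9.6.2.3 and state instead:
- **Cohort B (8.2.5):** a pre-specified model without selection. The full model held 94.1% coverage at about 7.4 events per parameter.
- **Cohort 1 (8.1.4):** likewise a pre-specified model if events allow; otherwise a reduced list, fixed before the outcome data are examined.
- **Cohort C (8.2.8):** a small pre-specified model of about one parameter per 10 re-initiation events, that is roughly 3 parameters at 30 events and 9 at 92. If geography is kept, use the three regions of section 9.6.2.5 (2 parameters) in place of 15 countries (14).
- **If any data-driven selection is kept:** repeat the whole selection inside bootstrap resamples, report inclusion frequencies, and label the selected factors exploratory instead of attaching ordinary 95% intervals. This option was not simulated here.

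The cost is protocol or analysis-plan wording, agreement on the covariate lists and, for the last option, some programming. No new data are needed. The price is fewer factors examined in Cohort C and wider intervals.
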